9.2 Handling of Missing Data

Missing data could occur due to various reasons, including missing visits/assessments, early withdrawal from the study, or missing due to COVID-19 infection or logistic restriction.

The COVID-19 pandemic is interfering with the conduct of many ongoing trials, with potential impacts on treatment duration and the collection, analysis and the interpretation of clinical trial data. Some protocol-specified visits in the clinical trials may be impacted due to COVID-19 infection or logistical restrictions during the pandemic. For example, some scheduled visits may be missed due to self-quarantine or local government restrictions on travel; some visits may also be delayed or canceled due to healthcare resource constraints during the pandemic. Impacted visits due to COVID-19 will be recorded in the database. The probability of having missed visits and missing data due to COVID-19 infection or logistical restrictions related to the COVID-19 pandemic can be reasonably assumed to be unrelated to the unobserved values. Therefore, for the purpose of statistical analysis, it is reasonable to assume that these missing data are missing at random (MAR) and the statistical models that require MAR assumption are appropriate.

Sensitivity analyses will be performed to assess the impact of missing data and the robustness of the conclusion.

Handling of missing data for the efficacy analyses is described below.

9.2.1 Categorical Endpoints

Non-Responder Imputation incorporating multiple imputation to handle missing data due to COVID-19 (NRI-C) will be the primary approach for handling missing data in the analysis of categorical endpoints. The NRI-C will categorize any subject who does not have an evaluation during a pre-specified visit window as a non-responder for the visit. The only exceptions are: 1) when the subject is a responder both before and after the visit window in the particular Study Period, the subject will be categorized as a responder for the visit; 2) missing data due to COVID-19 infection or logistical restriction will be handled by MI. Subjects who discontinue study drug due to lack of efficacy will be counted as non-responders at later visits. Subjects whose change/percent change from Baseline cannot be calculated because of a missing Baseline will be considered as a non-responder at all post-baseline visits, unless the post-baseline value is zero. More details are provided in [Appendix E](#).

Of note, during the Primary Analysis upon completion of Week 16, the NRI-C analysis will only be performed at all visits up to Week 16.

Multiple Imputation (MI) will be used as a sensitivity analysis for the primary endpoint at Week 16. PROC MI with the Markov Chain Monte Carlo (MCMC) statement will be first applied to generate 30 augmented datasets with monotonic missing pattern. The random seed for the MCMC will be the SAS numerical value of the first subject randomization date. PROC MI will then be used to impute 30 complete datasets using the regression method. The random seed for this imputation step will be the SAS numerical value of the last subject randomization date. The variables to be included in the imputation model are: treatment group, Baseline BSA, Baseline ppIGA category, and ppIGA measurements at each visit up to the end of the double blind Period A. The

imputed post-baseline measurements will be rounded to the same precision as the observed data to determine the responder status. Using the Cochran-Mantel-Haenszel (CMH) model adjusted by actual stratification factors (Baseline BSA category and Baseline ppIGA category), the imputed endpoints will be analyzed using each of the 30 datasets. SAS PROC MIANALYZE will be used to generate the final inferences of the risk difference between risankizumab and placebo. Note that measurements will be considered as missing after discontinuing study drug due to lack of efficacy before MI. Regardless of MI imputed values, subjects with a missing ppIGA assessment after discontinuation from study due to lack of efficacy will be counted as non-responders for these visits.

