Increases in major adverse cardiovascular events (MACE), including myocardial infarction, cerebrovascular accident, and cardiovascular death, reported initially with anti-IL-12/23 agents such as ustekinumab, have not been observed in longer-term studies with risankizumab. While the likelihood of increased MACE is small, all suspected cardiovascular or cerebrovascular events (serious or nonserious) observed in this study will be adjudicated by an independent Cardiovascular Adjudication Committee (CAC). The committee will remain blinded to treatment allocation (Section 6.2).

Local reactions to subcutaneously (SC) administered biologic therapies are usually limited to redness, swelling, or induration at the injection site. Manifestations of systemic hypersensitivity reactions include anaphylaxis, pruritus, hypotension, and respiratory distress. Both local and systemic hypersensitivity reactions are readily detectable, transient in nature, and manageable with standard medical treatment. Subjects will be closely monitored during study drug administration while at the site and be given instructions regarding management of signs and symptoms of anaphylaxis to be followed during home dosing visits. An independent Anaphylaxis Adjudication Committee (AAC) will adjudicate observed systemic hypersensitivity and anaphylactic events. The AAC will remain blinded to treatment allocation (Section 6.3).

In conclusion, the benefit-risk profile of risankizumab is considered appropriate for this stage of clinical development.²⁵ Based on data from the integrated safety analyses, risankizumab is safe and well tolerated and demonstrates a favorable benefit-risk profile.

For further details, please see findings from completed studies, including safety data, in the current risankizumab Investigator Brochure.¹⁷

In view of the coronavirus disease of 2019 (COVID-19) pandemic, the benefit-risk profile of various immunomodulatory therapies on COVID-19 is being evaluated based on real world data and clinical trial data. At this time, the effects of risankizumab on the course of COVID-19 are not well defined.

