10.2.2 Adverse Event Overview

An overview of TEAEs by treatment groups in each period will be presented consisting of the number and percentage of subjects experiencing at least one event for each of the following TEAE categories:

- Any treatment-emergent AE
- Any treatment-emergent AE related to study drug according to the investigator
- Any severe treatment-emergent AE
- Any serious treatment-emergent AE
- Any treatment-emergent AE leading to discontinuation of study drug
- Any treatment-emergent AE under the Areas of Safety Interest, as defined in [Appendix B](#)

- Any treatment-emergent AE leading to death
- Any COVID-19 related TEAEs

All deaths will also be summarized:

- COVID-19 related deaths
- Deaths occurring \leq 140 days after last dose of study drug
- Deaths occurring $>$ 140 days after last dose of study drug.

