2.0 Non-responder Imputation Incorporating Multiple Imputation (NRI)

2.1 Overall Description of the Method

For a dichotomized outcome variable with missing data, the NRI will categorize any subject who does not have evaluation during a pre-specified visit window as a non-responder for the visit, with two exceptions:

- If the subject is a responder both before and after the pre-specified visit window in the particular Study Period, the subject will be categorized as a responder for the visit.
- If the reason for missing (e.g., missed visits, incomplete visit, out-of-schedule visits, or discontinuations of study drug) is due to COVID-19, the information will be captured in the database and the subject's response status will be imputed using multiple imputation.

Subjects whose change/percent change from Baseline cannot be calculated because of a missing Baseline will be considered as a non-responder at all post-baseline visits, unless the post-baseline value is zero.

Non-responder imputation incorporating multiple imputation (NRI) for missing due to COVID-19 will be implemented as follows.

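### As worded, the COVID-19 missing-data rule would give a subject who dies of COVID-19 before Week 16 a fractional imputed response, while a death from any other cause is a non-response

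*SAP*

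**What the plan says.** **Default rule.** SAP 9.2.1: "The NRI-C will categorize any subject who does not have an evaluation during a pre-specified visit window as a non-responder for the visit".

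**Exceptions.** There are two, and 9.2.1 presents them as exhaustive. One covers a subject who responds both before and after the window in the same period. The other is that "missing data due to COVID-19 infection or logistical restriction will be handled by MI". Appendix E 2.1 repeats the second: where the reason for missingness "is due to COVID-19, the information will be captured in the database and the subject's response status will be imputed using multiple imputation".

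**Overrides to non-response.** SAP 9.2.1 states "Subjects who discontinue study drug due to lack of efficacy will be counted as non-responders at later visits". It also makes a subject with a missing Baseline a non-responder unless the post-baseline value is zero. Appendix E 2.4 restores non-response only where the reason is something other than COVID-19. The sample code does the same: the imputed status is replaced only when the Week 16 COVID-19 flag is not set to Y.

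**Sensitivity analysis.** All missing ppIGA values are multiply imputed. The one forced non-response is that "subjects with a missing ppIGA assessment after discontinuation from study due to lack of efficacy will be counted as non-responders".

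**Death.** Protocol 7.3, SAP 8.0 and SAP Tables 2 and 3 name one intercurrent event, discontinuation of study drug for lack of efficacy. Death appears in the SAP only under safety, where 10.2.2 plans a count of "COVID-19 related deaths".

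**The concern.** The endpoint is the achievement of clear or almost clear palms and soles at Week 16. A subject who has died has not achieved it. The missing-at-random argument in SAP 9.2 and Appendix E 1.1 concerns values that exist but were not observed, and its examples are quarantine, travel limits and healthcare constraints. After death there is no Week 16 value to recover.

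The wording also treats like cases differently. A death from pneumonia of another cause on Day 60 counts as failure, while a death from COVID-19 on the same day earns part of a response. Because treatment is in the imputation model, the part earned would be expected to be larger on risankizumab if the drug works. The protocol says that "the effects of risankizumab on the course of COVID-19 are not well defined", so the analysis should not leave the scoring of such a death to be settled after the fact. The same rule governs the four ranked secondary endpoints and the categorical summaries in Period B.

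**Working it through.** **The plan's own figure.** SAP 2.4 gives 75% against 45%, 84 per arm, two-sided 0.05 and power above 90%.

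- Pooled standard error under the null: √(2 × 0.60 × 0.40 / 84) = 0.0756.
- Standard error under the alternative: √((0.75 × 0.25 + 0.45 × 0.55) / 84) = 0.0720.
- z = (0.30 − 1.96 × 0.0756) / 0.0720 = 2.11, so power is 98.3%.
- Other versions give 98.6% (unpooled), 97.4% (continuity-corrected) and 97.3% (Fisher exact).

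The stated claim reproduces.

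**Tracing one record.** Take a randomized subject who attends Week 4 (Day 29) and dies on Day 60, before Week 16 (Day 113).

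1. The ITT Population is all randomized subjects (SAP 4.0), so the subject stays in the denominator.
2. Week 16 ppIGA is missing. The before-and-after exception cannot apply, because nothing is observed after death.
3. If the missingness is attributed to COVID-19 infection, the second exception applies and the non-responder override is skipped (Appendix E 2.4 and sample code).
4. Week 16 ppIGA is imputed from treatment, Baseline BSA, Baseline ppIGA category and Week 4 ppIGA, then rounded. Eligibility requires a Baseline ppIGA of at least 3, so any imputed 0 or 1 also meets the 2-point reduction.
5. Estimates are averaged over 30 datasets. The subject contributes the fraction of datasets in which the imputed score is a response.

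| Cause of death before Week 16 | Primary analysis (NRI-C) | MI sensitivity analysis |
|---|---|---|
| COVID-19 | Imputed | Imputed |
| Any other | Non-response | Imputed |

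(This assumes no earlier discontinuation for lack of efficacy, which would force non-response.)

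**Size of the credit, illustrative.** The documents give no Week 4 to Week 16 transition data and no expected number of COVID-19 deaths. Using the planning rates as an average credit, with 84 per arm and arms balanced within strata:

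- risankizumab: 0.75 / 84 = 0.89 percentage points per death;
- placebo: 0.45 / 84 = 0.54 percentage points per death.

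For a single subject the credit depends on Baseline and Week 4 scores. Assume a normal imputation distribution with SD 1.0, ignoring range limits. The chance that a draw rounds to 1 or less is Φ(1.5 − mean): 69%, 50%, 31% and 16% for means of 1.0, 1.5, 2.0 and 2.5.

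**Effect of scoring these deaths as non-response.** The numbers of deaths are assumed. With k deaths the arm's rate becomes rate × (84 − k) / 84.

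| Deaths k | Difference, risankizumab deaths only | Power, risankizumab deaths only | Power, k deaths in each arm |
|---|---|---|---|
| 0 | 30.0 points | 98.3% | 98.3% |
| 1 | 29.1 points | 97.6% | 98.0% |
| 2 | 28.2 points | 96.7% | 97.6% |
| 3 | 27.3 points | 95.6% | 97.3% |

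**The case against.** The best reply is that the trigger is inferred. The SAP never says that a COVID-19 death is to be flagged as COVID-19 missingness. Appendix E 2.1 illustrates the trigger with visit and dosing problems: "If the reason for missing (e.g., missed visits, incomplete visit, out-of-schedule visits, or discontinuations of study drug) is due to COVID-19". Death has its own eCRF in the protocol, and the sample code omits the step that merges the COVID-19 flag. This stands as far as it goes: the documents show no intention to credit deaths. But infection itself is a named reason, the examples are not exclusive, and nothing excludes a fatal infection. A programmer who scored the death as failure would be departing from the two written exceptions.

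Several stronger readings are tempting and are not supported:

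- **That such a subject is counted as a responder.** MI gives a fraction, not a full response.
- **That most of the imputed scores would be 0 or 1.** Under the assumed imputation means above, the chance per dataset runs from 16% to 69%.
- **That 0.75 and 0.45 are the credit for a particular subject.** They are marginal planning rates, whereas imputation conditions on Baseline and Week 4 values.
- **That a fatal harm is hidden as benefit.** Deaths, COVID-19-related deaths and serious events are reported separately under safety (SAP 10.2.2 and 10.2.5).
- **That having treatment in the imputation model is itself a bias.** It is a normal part of MI under missing at random. The fault is applying MI where no value exists.

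It is also fair to say that the sensitivity analysis relaxes non-responder imputation on purpose. That explains imputing missed visits, but it does not give a deceased subject a Week 16 score.

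**Conclusion.** The point holds, and the rule is wrong as written rather than merely short on detail: if followed literally, it returns an unsuitable value whenever it is triggered. This rests on reading data missing because of COVID-19 infection as including data missing because the infection was fatal, which the wording covers and nothing excludes.

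The consequence is small. At the planning rates it is about 0.9 points per death on risankizumab or 0.5 on placebo, with offsetting effects if deaths occur in both arms. It is exactly zero in NRI-C if no COVID-19 death occurs. A reader might infer that the primary conclusion is at risk. It is not: even with three such deaths, all on risankizumab and all rescored as non-response, power at the planning rates is 95.6%, above the stated 90%. This is a low-priority correction to the handling of an intercurrent event, worth making because it is cheap.

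**What to change.** - **Intercurrent-event text.** In SAP 8.0 and Tables 2 and 3, and in protocol 7.3 if it is amended, state that death from any cause, including COVID-19, is non-response at all later scheduled visits under the composite strategy. Changing only the missing-data section would leave the estimand and the analysis in disagreement.
- **Missing-data text.** Put the same statement in SAP 9.2.1 and Appendix E 2.1 and 2.4, and add that MI for COVID-19 missingness applies only to subjects alive at the scheduled visit.
- **Sensitivity analysis.** Apply the death override next to the existing lack-of-efficacy override.
- **Code.** Set response to 0 from a death flag, or by comparing the death date with the scheduled (target) visit day. The actual visit date will not serve, because a visit that did not take place has none.

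The cost is a sentence in each of these places and one override step in the program. The reported response rate would be slightly lower if such a death occurred, and the NRI-C results would be unchanged otherwise.

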5.6 Follow-Up After Subject Discontinuation of Study Drug or from Study

To minimize missing data for safety and efficacy assessments, subjects who prematurely discontinue study drug treatment should continue to be followed for all regularly scheduled visits, unless subjects have decided to discontinue the study participation entirely (withdrawal of informed consent). Subjects should be advised on the continued scientific importance of their data even if they discontinue treatment with study drug early.

If a subject prematurely discontinues study participation, the procedures outlined for the PD visit should be completed as soon as possible, preferably within 2 weeks. In addition, if subject is willing, a follow-up phone call 140 days after the last dose of study drug may be completed to ensure all treatment-emergent AEs/serious adverse events (SAEs) have been resolved. The 140-day follow-up phone call following the last dose administration of risankizumab study drug during the trial will not be required for any subject who initiates commercially available risankizumab after completion of the Week 52 visit or premature discontinuation visit.

If a subject withdraws from study follow-up or withdraws permission for the collection of their personal data, the study staff may still use available public records to obtain information about survival status only, as appropriate per local regulations.

In the event a subject withdraws consent from the clinical study, biomarker research will continue unless the subject explicitly requests analysis to be stopped. When AbbVie is informed the subject has withdrawn and no longer wishes biomarker sample research to continue, samples will not be analyzed, and no new biomarker analysis data will be collected for the withdrawn subject or added to the existing data or database(s). A subject may withdraw consent for optional biomarker research at any time and remain in the clinical study. Data generated from clinical study and/or optional biomarker research, before subject withdrawal of consent, will remain part of the study results.

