2.0 Study Design and Objectives

2.1 Objectives, Hypotheses and Estimands

The primary objective of this study is to assess the safety and efficacy of risankizumab (150 mg) versus placebo for the treatment of signs and symptoms of moderate to severe plaque psoriasis in patients with (non-pustular) palmoplantar involvement.

Primary Efficacy

The primary efficacy objective is to demonstrate a higher rate of Palmoplantar Investigator's Global Assessment (ppIGA) of "clear" or "almost clear" (0 or 1) with at least a 2-point reduction from Baseline at Week 16 of treatment with risankizumab

(150 mg) compared to placebo in the Intent-to-Treat (ITT) Population, which consists of all randomized subjects (Section 5.0).

The hypothesis corresponding to the primary endpoint is:

- The proportion of subjects achieving ppIGA of 0 or 1 with at least a 2-point reduction from Baseline with risankizumab is greater than that with placebo at Week 16.

The estimand corresponding to the primary endpoint is defined using composite variable strategy:

- Difference in the proportion of subjects achieving ppIGA of 0 or 1 with at least a 2-point reduction from Baseline at Week 16 without premature discontinuation of study drug due to lack of efficacy prior to Week 16, in the risankizumab group in comparison with the placebo group in the ITT population.

Secondary Efficacy

The secondary efficacy objectives are based on the ranked secondary endpoints as defined in Section 3.2. The hypotheses and estimands corresponding to these ranked secondary endpoints are summarized in Table 1.

Table 1. Hypotheses and Estimands Corresponding to the Ranked Secondary Endpoints

Hypothesis	Estimand
1. The proportion of subjects achieving PPASI 75 with risankizumab is greater than that with placebo at Week 16.	Difference in the proportion of subjects achieving PPASI 75 at Week 16 without premature discontinuation of study drug due to lack of efficacy prior to Week 16 in the risankizumab group in comparison with the placebo group in the ITT population.
2. The proportion of subjects achieving PPASI 90 with risankizumab is greater than that with placebo at Week 16.	Difference in the proportion of subjects achieving PPASI 90 at Week 16 without premature discontinuation of study drug due to lack of efficacy prior to Week 16 in the risankizumab group in comparison with the placebo group in the ITT population.

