7.3 Prior and Concomitant Medications

Prior and concomitant medications will be summarized by generic names. A prior medication is defined as any medication taken prior to the first dose date of study drug. A concomitant medication is defined as any medication that is started prior to the first dose date of study drug and continued to be taken on or after the first dose date of study drug, or any medication that is started on or after the first dose date of study drug, but not after the last dose date of study drug plus 140 days. The number and percentage of subjects taking medications will be summarized by generic drug names based on the World Health Organization (WHO) Drug Dictionary for both prior and concomitant medications.

In addition, subjects' prior biologic therapy for psoriasis will also be summarized by the reason for discontinuation.

Prior and concomitant medications will be summarized among the ITT Population.

8.0 Handling of Potential Intercurrent Events for the Primary Endpoint and Key Secondary Endpoints

The primary efficacy endpoint (defined in Section 3.1) and four ranked secondary endpoints (defined in Section 3.2), will be analyzed in the ITT Population and the following method will be used to address the potential intercurrent event:

- Subjects who discontinue study drug due to lack of efficacy prior to Week 16 will be considered as non-responders at Week 16.

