9.3.3 Sensitivity and Supplementary Analyses of the Primary Efficacy Endpoint

A sensitivity analysis using MI to handle missing data will be performed on the primary endpoint, as defined in Section 9.2.1. Treatment, Baseline BSA, and the observed ppIGA assessments at all Baseline and post-baseline visits will be included in the imputation model.

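### The MI sensitivity analysis forces non-response only after lack-of-efficacy discontinuation from the study, whereas the estimand counts discontinuation of study drug; Appendix E omits the rule for NRI-C

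*SAP*

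**What the plan says.** **Estimand and intercurrent event.** SAP Section 2.1 defines response under a composite strategy, as achieving the ppIGA criterion "without premature discontinuation of study drug due to lack of efficacy prior to Week 16". Section 8.0 applies the same trigger: "Subjects who discontinue study drug due to lack of efficacy prior to Week 16 will be considered as non-responders at Week 16". Table 2 in Section 9.3.2 repeats it.

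**NRI-C (main analysis).** Section 9.2.1 again names study drug, with no COVID-19 exception: "Subjects who discontinue study drug due to lack of efficacy will be counted as non-responders at later visits". It then refers to Appendix E for detail.

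**MI (sensitivity analysis).** Section 9.3.3 states: "A sensitivity analysis using MI to handle missing data will be performed on the primary endpoint", and points back to Section 9.2.1 for the method. There, one sentence says that "measurements will be considered as missing after discontinuing study drug due to lack of efficacy before MI". The next says that, whatever the imputed value, "subjects with a missing ppIGA assessment after discontinuation from study due to lack of efficacy will be counted as non-responders".

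**Follow-up.** Protocol Section 5.6 says that "subjects who prematurely discontinue study drug treatment should continue to be followed for all regularly scheduled visits", unless they leave the study altogether. SAP Section 5.0 also tabulates study-drug discontinuation separately from the end of study participation.

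**Appendix E.** Sections 2.1 and 2.4 turn missing assessments into non-response, with a before-and-after exception and a COVID-19 exception. The COVID-19 exception extends to drug stopping: where the reason for missingness (including "discontinuations of study drug) is due to COVID-19, the information will be captured in the database"), response status is multiply imputed. Lack of efficacy is not mentioned anywhere in Appendix E.

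**The concern.** Two consecutive sentences on MI use different triggers. Scores are removed after stopping study drug for lack of efficacy, but non-response is forced only after leaving the study for that reason. Because the protocol separates the two events, some subjects can meet the first condition and not the second. Their observed Week 16 score would be deleted and replaced by a missing-at-random draw that may be a response. The composite estimand excludes that outcome.

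MI is the only sensitivity analysis specified for the primary endpoint. As written, it would change the handling of the intercurrent event along with the handling of missing data, so a difference from the main result could not be put down to missing data alone.

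For NRI-C, a programmer who works from Appendix E instead of Section 9.2.1 would apply a different rule to subjects who stop drug for lack of efficacy.

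**Working it through.** **1. The rules side by side**

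| Place | Event that forces non-response |
|---|---|
| SAP 2.1, 8.0, Table 2 | Stopping study drug for lack of efficacy before Week 16 |
| SAP 9.2.1, NRI-C | Stopping study drug for lack of efficacy |
| SAP 9.2.1, MI, scores set to missing | Stopping study drug for lack of efficacy |
| SAP 9.2.1, MI, forced non-response | Leaving the study for lack of efficacy |
| SAP Appendix E 2.1, 2.4 | Missing for a reason other than COVID-19; no lack-of-efficacy rule |

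Take a subject who stops drug for lack of efficacy and attends Week 16. NRI-C in the SAP body gives non-response. MI, read literally, gives an imputed status.

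Now take a subject who stops drug for lack of efficacy and misses Week 16 because of COVID-19. The SAP body gives non-response. Appendix E gives an imputed status.

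**2. The sample code (Appendix E, Section 3.0)**

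The override to non-responder imputation depends only on the COVID-19 flag, so the MI value stays whenever the flag is `Y`. The override is written to dataset `ALLF`, but the `PROC FREQ` step that starts the analysis reads `ALL`. That suits MI, which is told to skip the override block. For NRI-C, as printed, the override never reaches the analysis.

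**3. The plan's own power figure**

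Inputs from SAP 2.4: 75% against 45%, n = 84 per arm, two-sided alpha 0.05, stated power above 90%.

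Power = Φ{[d − 1.96·√(2p̄(1−p̄)/n)] / √[(p₁(1−p₁) + p₀(1−p₀))/n]}

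With d = 0.30 and p̄ = 0.60: (0.30 − 1.96 × 0.0756)/0.0720 = 2.11, so power = 98.3%. The stated figure is reproduced.

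**4. Size of the shift if the MI text is applied literally**

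The documents give no lack-of-efficacy discontinuation rate, so every count below is an assumption. Let k be the number of affected subjects who stay in the study and p their imputed response probability (subscript R for risankizumab, P for placebo).

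Shift in points = 100 × (k_R·p_R − k_P·p_P)/84

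With placebo subjects only:

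| k_P | p_P | Shift | Difference | Power |
|---|---|---|---|---|
| 0 | – | 0 | 30.0 | 98.3% |
| 4 | 0.10 | −0.48 | 29.5 | – |
| 4 | 0.45 | −2.14 | 27.9 | 96.5% |
| 8 | 0.10 | −0.95 | 29.0 | – |
| 8 | 0.45 | −4.29 | 25.7 | 93.7% |

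A probability of 0.45 is the whole-arm placebo rate and so an upper end. A harsher case has 15% of placebo and 2% of risankizumab subjects affected, with imputed probabilities of 0.60 and 0.90. It gives 76.8% against 54.0%, a difference of 22.8 points and power of 88.1%.

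**5. A more realistic imputed probability**

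The planned normal-regression MI was simulated with 600 trials, 84 per arm and 30 imputations. Week 16 ppIGA was regressed on treatment, BSA, baseline ppIGA and Week 4 ppIGA, with draws limited to 0–4 and rounded. Assumed: Week 16 response 75% against 45%; Week 4 ppIGA 0/1 in 25% against 10%; discontinuers drawn from Week 16 non-responders with Week 4 ppIGA of 3 or more.

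| Week 4 to Week 16 correlation | p_P | p_R | Shift, 4 PBO / 0 RZB | Shift, 4 / 1 | Shift, 2 / 2 |
|---|---|---|---|---|---|
| 0.3 | 0.33 | 0.49 | −1.57 | −1.03 | +0.39 |
| 0.5 | 0.28 | 0.42 | −1.33 | −0.85 | +0.35 |
| 0.7 | 0.22 | 0.33 | −1.02 | −0.65 | +0.26 |

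Because treatment is in the imputation model, p_R exceeds p_P. The shift favours risankizumab when k_R/k_P is above p_P/p_R, which is about 0.67 in each row (for example 0.33/0.49).

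**The case against.** The best defence is that Section 8.0, Table 2 and the estimand attach the study-drug rule to the primary endpoint itself, whichever missing-data method is used. On that view the MI sentence is a slip: it refers to the values the previous sentence has just set to missing, and no text states an aim of replacing an observed score with a random draw. That is probably what was intended. But Section 9.2.1 is the text that specifies MI, and a change of wording between adjacent sentences can be taken as deliberate.

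On NRI-C, the SAP body states the rule, and Appendix E is only supporting detail that contains no contrary lack-of-efficacy rule. A code comment says the traditional NRI variable covers special handling, with the before-and-after exception given only as an example, so it may already carry the rule. That helps when the COVID-19 flag is not set. It does not help when the flag is `Y`, because the variable is then not used. This overlap is likely to be rare. The `ALL`/`ALLF` mismatch is a separate defect in code labelled as a sample, written for PPASI 75, with the COVID-19 merge step omitted. It does not show that the primary analysis will be wrong.

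On size, the objection largely stands. Period A has one scheduled dose after Baseline, so there is little opportunity to stop for lack of efficacy. With 1 or 2 placebo subjects at p = 0.33, the shift is 0.4 to 0.8 points. The simulation rests on assumed inputs and is illustrative. The power figures use a complete-data formula and leave out between-imputation variance, so they are not the power of the MI analysis.

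**Conclusion.** The concern holds. As written, the MI rule lets subjects who stop study drug for lack of efficacy but stay in the study count as responders, contrary to the composite estimand. For NRI-C there is a gap between the SAP body and Appendix E, plus a dataset error in the sample code; neither amounts to a planned error in the primary analysis.

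The likely numerical effect is small and mainly conservative. In the placebo-only scenarios of Step 4 the difference stays between 29.5 and 25.7 points, and the approximate power does not fall below 93.7%. The harsher 88.1% case needs imputed response probabilities above the assumed whole-arm rates. The sign turns in favour of risankizumab only when the affected counts are similar in the two arms or higher on risankizumab. All of this depends on assumed counts. The case for correction rests on consistency with the estimand and on keeping the sensitivity analysis interpretable; the primary conclusion is not under threat.

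**What to change.** - **SAP 9.2.1, MI paragraph:** in the override sentence, change the event from discontinuation from the study to discontinuation of study drug due to lack of efficacy.
- **Appendix E 2.1 and 2.4:** state that the lack-of-efficacy rule takes precedence over the COVID-19 exception and also applies to observed values.
- **Sample code, NRI-C:** add a lack-of-efficacy flag, for example `IF COVID19_16 NE 'Y' OR LOE_BEFORE_16='Y' THEN PPASI75_16=PPASI75NRI_16;`, with `PPASI75NRI_16=0` for these subjects, and have the NRI-C analysis read `ALLF`.
- **Sample code, MI:** because MI skips that block, set the response to 0 in `ALL` when `LOE_BEFORE_16='Y'`, before `PROC FREQ`.

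The cost is a few words, one sentence and three lines of code. No new data are needed, since SAP Section 5.0 already summarises the primary reason for stopping study drug. The sample size and the stated power do not change.
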